## **3 Study Design**

### **3.1 General Design**

This is a prospective interventional pilot study assessing the safety and tolerability, as well as efficacy of the use of VNS in patients with idiopathic and functional gastroparesis. We will also include patients with functional dyspepsia, which have almost identical clinical symptomatology and are believed to share similar underlying inflammation and dysautonomia. We plan to recruit a total of 45 patients, 15 patients of each subgroup, for 4 weeks of therapy with VNS. Patients will undergo baseline measures of symptoms, gastric emptying testing, vagal tone, and inflammation. After enrollment, patients will undergo two upper endoscopies (pre and post therapy). Pt will be seen in clinic for recruitment, day 0, for follow-up at 4 weeks, and again at 8 weeks, for a total of six visits including their appointed endoscopy days.

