### **3.2 Study Objectives**

1. Establish the effect of VNS on gastric emptying time and on cardinal symptoms of gastroparesis (nausea, vomiting, bloating, abdominal pain, and early satiety).
2. Assess the effects of VNS on various measures of quality of life, including global health and overall pain interference.
3. Investigate molecular and neuroimmune signaling pathways in different gastroparesis patients.
4. Determine the effects of VNS on measurable serum inflammatory markers and cytokines.
5. Determine the effects of VNS on measurable cytokines, nerve growth factors, and neurotransmitters in the gastric and duodenal submucosa.
6. To characterize the submucosal enteric nervous system in gastroparesis subtypes and identify novel neuro-immune interactions.
7. Determine if gastric emptying and symptom response to VNS is associated with changes in inflammatory markers and neuro-immune signaling.
8. Determine if there is a difference in response to VNS in patients with idiopathic vs. diabetic gastroparesis.
9. Evaluate the safety and tolerability of VNS therapy in patients with gastroparesis and functional dyspepsia.

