### **3.3 *Study Endpoints***

#### ***I. Primary Study Endpoints***

- 1.1 The primary outcome measure will be the effect of VNS on gastroparesis cardinal symptoms as measured by the gastroparesis cardinal symptom index (GCSI) questionnaire.
- 1.2 The second primary outcome measure will be the effect of VNS on gastric emptying time as measured by the gastric emptying spirulina breath test.

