#### ***4.2 Sample size justification***

- Total of 45 patients; 15 with functional dyspepsia, 15 with diabetic gastroparesis, and 15 with idiopathic gastroparesis.
- Primary comparison: Gastric emptying half time score and GCSI, pre and post VNS
- Error protection: Type I = 0.05 two-sided and Type II = 0.10 (80% power). To detect a clinically significant change of >30% in gastric emptying time, and a reduction in  $\geq 1$  GCSI aggregate.

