## **7. Statistical Analysis Plan**

The mean baseline GCSI aggregate score will be compared with the mean aggregate score at the end of each treatment week, and in the 4 subsequent weeks after therapy discontinuation. Paired Student T-tests will be done comparing baseline with all other subsequent time points. Gastric emptying times will be plotted before treatment, at the end of treatment, and four weeks after end of treatment and compared by ANOVA. Similarly, differences among the three subgroups of patients will be determined at baseline and after treatment.

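### GCSI paired t-test omits diagnosis although recruitment is in fixed quotas of 15: if change differs by diagnosis, the interval is wider than the design warrants and some power is lost

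*Combined protocol and SAP*

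**What the plan says.** Section 3.1 sets the sampling scheme: "We plan to recruit a total of 45 patients, 15 patients of each subgroup, for 4 weeks of therapy with VNS". Section 4.2 repeats the quotas as "15 with functional dyspepsia, 15 with diabetic gastroparesis, and 15 with idiopathic gastroparesis".

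Section 3.3 makes the GCSI the first primary endpoint ("The primary outcome measure will be the effect of VNS on gastroparesis cardinal symptoms") and gastric emptying time the second. Section 4.2 names the main contrast without reference to diagnosis: "Primary comparison: Gastric emptying half time score and GCSI, pre and post VNS".

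Section 7 gives the GCSI analysis in one sentence: "Paired Student T-tests will be done comparing baseline with all other subsequent time points". Gastric emptying at three visits is compared by ANOVA, with no factors listed. The last sentence of Section 7 adds a separate comparison of the three diagnoses, before and after therapy. Objective 8 in Section 3.2 asks a related question: "Determine if there is a difference in response to VNS in patients with idiopathic vs. diabetic gastroparesis".

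No section brings diagnosis into the overall pre/post test.

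**The concern.** The sample is stratified by design. With 15 patients fixed in each diagnosis, the overall mean change is an equally weighted mean of three stratum means, and its sampling variance comes only from variation within diagnoses. A paired t-test on all 45 changes treats them as one simple random sample, so its standard error also absorbs any spread among the three diagnosis means. Pairing removes differences in baseline level but not differences in change. The separate subgroup comparison leaves this standard error as it is.

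At stake is the precision of the first primary result. In a pilot of 45 patients, the interval around the mean change is one of the main things the trial delivers, and it should match the way the patients were sampled.

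**Working it through.** **Inputs.** From the documents: n = 45 as 3 × 15 (Sections 3.1 and 4.2); two-sided alpha 0.05; a GCSI reduction of at least 1 (Section 4.2). For power, Section 4.2 says "Error protection: Type I = 0.05 two-sided and Type II = 0.10 (80% power". A Type II error of 0.10 means 90% power, so both 80% and 90% are used below. Not given: the SD of change, and R² (the share of the variance of change that lies between diagnoses). Both are assumptions, shown over a range.

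**The plan's own figure.** Power for a paired t-test with 44 df, from the noncentral t:
- 80% power needs a noncentrality of 2.865, a standardised change of 2.865/√45 = 0.427. A 1-point change then implies an SD of 1/0.427 = 2.34.
- 90% power needs a standardised change of 0.494, implying an SD of 2.02.

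With no SD stated, 45 can be neither confirmed nor refuted.

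**Interval width.** Let Vw be the within-diagnosis variance of change and Vb the variance of the three diagnosis means, so R² = Vb/(Vw + Vb). The design variance of the mean is Vw/45. The plain t-test estimates, in expectation, [Vw + (45/44)Vb]/45. The ratio of half-widths is therefore √{[Vw + (45/44)Vb]/Vw} × t44/t42, where t44/t42 = 2.0154/2.0181 = 0.9987. At R² = 0.10: √[(0.90 + 0.1023)/0.90] × 0.9987 = 1.055 × 0.9987 = 1.054, about 5% too wide.

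**Power.** Scale the effect so that the noncentrality is 2.865 against the total variance. The adjusted test then has noncentrality 2.865/√(1 − R²) on 42 df. The unadjusted test's power was simulated under fixed quotas with one diagnosis differing from the other two. It does not stay at 80%: the mean varies less than the test assumes, so its power rises slightly.

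| R² | Unadjusted power | Adjusted power | Gain (points) | Interval too wide by |
|---|---|---|---|---|
| 0.05 | about 80.5% | 81.9% | 1.3 | 3% |
| 0.10 | 81.2% | 83.9% | 2.7 | 5% |
| 0.13 | 81.5% | 85.1% | 3.5 | 7% |
| 0.20 | 82.3% | 87.9% | 5.4 | 12% |
| 0.25 | 83.0% | 89.8% | 6.8 | 16% |

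Gains are simulated and can differ from column subtraction by up to 0.2 points. Starting from 90%, the same calculation gives gains of about 0.8, 1.6, 2.1, 2.9 and 3.4 points.

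**What these R² values mean.** If one diagnosis differs from the other two by d within-diagnosis SDs, R² = (2/9)d²/[1 + (2/9)d²]. This is 0.05 at d = 0.5, 0.11 at d = 0.75 and 0.18 at d = 1.

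**At a mean GCSI change of 1 point**, with assumed within-diagnosis SDs:
- SD 2, diagnosis means 0.5/1/1.5: interval 2% wider; power 90.0% plain, 90.6% adjusted.
- SD 2, means 0/1/2: interval 8% wider; 87.9% against 90.9%.
- SD 1.5, means 0/1/2: interval 14% wider; 98.3% against 99.2%.

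**If diagnosis has no effect.** The adjusted test has 79.9% power against 80.0%, a cost of about 0.1 point.

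**The case against.** The strongest reply is that this is a conditional matter of efficiency. The paired t-test is valid, and no section says that change differs by diagnosis. Objective 8 only asks the question, and only for idiopathic against diabetic patients. Section 3.1 points the other way for functional dyspepsia, describing nearly the same symptoms and a presumed shared biology. If the SD of change is 1.5 or less, power for a 1-point change is at least 98% with either analysis. All of this stands, and it limits the size of the point. It does not remove the mismatch between the sampling scheme and the standard error, which can widen the interval even where power is ample.

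The pooled reading is also an inference. Section 7 does not say that the t-tests use all 45 patients, and paired tests run within each diagnosis would not have this problem. Still, pooling is the plain reading, because the sentence names no subgroup and diagnosis appears only in a later, separate comparison.

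A reader might infer that the true two-sided error of the planned test is about 3.9% (R² = 0.10) or 2.4% (R² = 0.25). Those figures require an overall mean change of exactly zero with improvement in one diagnosis offset by worsening in another. If no diagnosis changes at all, the plain test keeps its nominal 5%.

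Equal weighting is also a choice. With unequal numbers of completers it estimates the average over diagnoses rather than over patients. That is a real change of target and has to be stated.

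**Conclusion.** The point holds for the GCSI as a cheap improvement. If mean change differs by diagnosis, the pooled paired t-test gives an interval about 3% to 16% wider than the design warrants for R² between 0.05 and 0.25. It gives up about 1.3 to 6.8 points of power from a starting point near 80%, and less from 90%. A 5-point gain needs R² just below 0.20, which is one diagnosis differing from the others by about 1 within-diagnosis SD. If change does not differ, nothing is lost.

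These figures rest on the pooled reading, on 15 patients analysed per diagnosis, on normally distributed changes with equal within-diagnosis variance, and on assumed R² and SD.

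Stronger readings are not supported. The documents do not show that power will be lost, since they give no difference in change by diagnosis. The error is conservative, so it does not create false claims of benefit. The paired-test figures do not carry over to gastric emptying, which is compared by an ANOVA whose factors are not stated.

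**What to change.** In Section 7, analyse the within-patient GCSI change from baseline to each time point with a linear model that has diagnosis as a three-level fixed factor. Report the equally weighted mean change over the three diagnoses, with its interval from the within-diagnosis residual (45 − 3 = 42 df with complete data). Keep the plain paired t-test as a sensitivity analysis. For gastric emptying, use the same diagnosis-adjusted model for the change from baseline to end of treatment. State that, if completers are unequal across diagnoses, the estimate is the diagnosis-average rather than the patient-average change. If paired tests within each diagnosis are what is intended, Section 7 should say so, and the point falls away for those tests.

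The cost is a sentence or two of SAP wording, fixed before the data are seen so that the adjustment cannot look chosen afterwards. No new data are needed, because diagnosis is established at entry. The statistical price is 2 degrees of freedom, about 0.1 power point if diagnosis has no effect on change.

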6. Patients will present to endoscopy for their post-treatment upper endoscopy 4 weeks after initiation of therapy. No later than 3 days after endoscopy, patients will present to clinic at which time post-treatment gastric emptying testing, HRV testing, and laboratory tests (blood and stool) will be obtained, and the aforementioned forms will again be completed.
7. Patients will be seen in clinic again at 4 weeks after discontinuation of therapy, and undergo a repeat medical history and physical exam. At this time gastric emptying testing, HRV testing, and laboratory tests (blood and stool) will again be obtained; and the aforementioned forms will again be completed to assess whether any change in symptoms and disease severity has occurred off therapy.

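### Gastric emptying, a primary endpoint with a pre/post comparison, is given only a three-visit ANOVA of unstated type, and no test of that comparison is stated

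*Combined protocol and SAP*

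**What the plan says.** - **Endpoint.** Section 3.3 gives gastric emptying primary status: "The second primary outcome measure will be the effect of VNS on gastric emptying time as measured by the gastric emptying spirulina breath test".
- **Comparison.** Section 4.2 states: "Primary comparison: Gastric emptying half time score and GCSI, pre and post VNS". It sets a two-sided Type I error of 0.05 and a target change of more than 30% in gastric emptying time, with 45 patients in three groups of 15.
- **Which visit is post.** Section 5.2 describes the visit within 3 days of the week-4 endoscopy: "patients will present to clinic at which time post-treatment gastric emptying testing". A further test comes four weeks after VNS stops, with the forms repeated "to assess whether any change in symptoms and disease severity has occurred off therapy".
- **Analysis.** Section 7 is one paragraph. It first describes the GCSI comparison, then says: "Paired Student T-tests will be done comparing baseline with all other subsequent time points". Only after that does it mention gastric emptying: "Gastric emptying times will be plotted before treatment, at the end of treatment, and four weeks after end of treatment and compared by ANOVA". It gives no ANOVA type, contrast or follow-up test for this endpoint.

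**The concern.** The comparison is specified but its test is not. An ANOVA over three visits asks whether any of the three means differ. Section 4.2 asks whether one particular pair differs.

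The ANOVA sentence can be read in two ways, and neither tests that pair:

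- **Repeated-measures ANOVA.** The overall F-test can be significant because of the off-therapy visit alone, or lose power when the off-therapy value lies between the other two.
- **Ordinary one-way ANOVA.** This treats three measurements on the same patients as three independent groups, so differences between patients stay in the error term.

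Followed as written, the plan would give a primary endpoint a p-value that does not answer its stated question. An analyst could add the pre/post comparison later, but that step would be chosen outside the SAP.

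**Working it through.** **Inputs from the documents.** N = 45 (15 per group), two-sided 0.05, three gastric emptying visits. The sample size cannot be reproduced: no SD, within-patient correlation or dropout rate is given. Section 4.2 also gives two power levels ("Error protection: Type I = 0.05 two-sided and Type II = 0.10 (80% power"); I use 80% and show 90% at the end.

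**Assumptions.** Unit variance at each visit; equal correlation ρ between visits of 0.3, 0.5 or 0.7 unless stated.

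**Step 1. Size the effect.** Let dz be the mean change divided by the SD of change. Solving the noncentral t (df n − 1) for 80% power gives dz = 0.427 at N = 45 and 0.778 at N = 15. In units of the visit SD, δ = dz·√(2(1 − ρ)).

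**Step 2. Repeated-measures overall F-test.** The noncentrality is λ = n·Σ(μ − mean)²/(1 − ρ), with df 2 and 2(n − 1).

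- Effect fully returns or fully persists off therapy: Σ = (2/3)δ², so λ = (4/3)·n·dz². At N = 45, (4/3) × 45 × 0.427² = 10.94.
- Half persists: Σ = δ²/2, so λ = n·dz². At N = 45, 45 × 0.427² = 8.21.

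ρ cancels only under equal variances and correlations.

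| Power (paired test = 80%) | N = 45 | N = 15 |
|---|---|---|
| Overall F, full return or full persistence | 84% | 85% |
| Overall F, half persists | 71% | 73% |
| Overall F then paired test, full return or persistence | 76% | 76% |
| Overall F then paired test, half persists | 70% | 71% |

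The last two rows are simulated and require both tests to be significant. With no change at any visit, this two-step rule rejects about 2.5% of the time.

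**Step 3. Stress case.** Suppose there is no end-of-treatment change and only the off-therapy visit shifts. The documents do not predict this; it shows what the F-test responds to. At N = 45 a shift of δ gives λ = 10.94 again, and the overall test rejects 84% of the time. For shifts of three-quarters, half and a quarter of δ it rejects 58%, 29% and 10%. The paired pre/post test rejects 5%.

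**Step 4. Ordinary one-way ANOVA.** The variance relevant to visit differences is 1 − ρ, but this ANOVA uses an error term of about 1. It is too large by 1/(1 − ρ): 1.43, 2 and 3.33 at ρ = 0.3, 0.5 and 0.7. Simulated results:

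| | ρ = 0.3 | ρ = 0.5 | ρ = 0.7 |
|---|---|---|---|
| Type I error, N = 45 | 1.5% | 0.3% | 0.02% |
| Power, full return or persistence, N = 45 | 69–70% | 49% | 16% |
| Power, half persists, N = 45 | 53% | 32% | 8% |
| Type I error, N = 15 | 1.7% | 0.5% | 0.05% |
| Power, full return or persistence, N = 15 | 72% | 53% | 22% |
| Power, half persists, N = 15 | 57% | 36% | 12% |

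**Step 5. The protocol's 30% change**, with full return and ρ from 0.3 to 0.8:

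- N = 45, SD 30–40% of the mean: both tests have 98% power or more.
- N = 45, SD 60% of the mean: one-way ANOVA 68–73%, paired test 79% to over 99%.
- N = 15, SD 40% of the mean: one-way ANOVA 44–51%, paired test 63–99%.

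**Step 6. Sensitivity.** Three unequal-correlation patterns were tried at N = 45 (baseline–end, baseline–off, end–off: 0.7, 0.5, 0.7; 0.6, 0.3, 0.6; 0.7, 0.3, 0.5). The overall test rejects 57–73% in the stress case, has 51–81% power for real effects, and has 49–72% when followed by the paired test. If 90% power is used instead (dz = 0.494, N = 45), the overall test has 93% (full return or persistence) and 84% (half persists), followed by the paired test about 88% and 83%. One-way ANOVA then has 84%, 68% and 30% at ρ = 0.3, 0.5 and 0.7.

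**The case against.** **The paired t-test sentence names no endpoint.** Section 4.2 lists both endpoints under one pre/post comparison, so a generous reader could apply the t-tests to gastric emptying too. That reading is possible but not the plain one: the sentence continues the GCSI description, and gastric emptying then gets its own sentence and its own method. If the generous reading was intended, the endpoint would have two tests and no rule for which decides, so the same edit is needed.

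**A competent analyst would use repeated measures and then compare pre with post.** This is likely, and it is the natural choice for patients measured repeatedly. False pre/post claims would then stay near 5% or below. Under equal correlations the cost is 4 to 10 points of power. But the step is not written in the SAP.

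**The one-way branch is hypothetical and conservative.** This stands in part. The documents never say one-way, and its error rate is below 5%, so it cannot inflate positive claims. At N = 45 with an SD of 30–40% of the mean it costs almost nothing for a 30% change. The risk is a missed change when variability is larger or when groups of 15 are tested separately.

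**A planned contrast in a repeated-measures or mixed model would serve as well as a paired t-test.** This stands, and the fix allows it.

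**Conclusion.** The concern holds. The only method expressly tied to gastric emptying is a three-visit ANOVA of unstated type, and nothing else in the document supplies a test of the stated pre/post comparison. This follows from the text and needs no assumed figure.

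Its size does depend on assumed variances and correlations. Under the repeated-measures reading the power difference is modest and can go either way; the main fault is that a significant result would not answer the stated question. Under the one-way reading the power loss ranges from negligible to severe, depending on the SD and the correlation.

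This should be corrected before results are seen. The single-arm pilot design limits the consequence, since no pre/post test here can attribute a change to VNS.

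**What to change.** Replace the gastric emptying sentence in section 7 with wording such as:

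> The primary gastric emptying test is a paired t-test of the within-patient change in half time, on the original scale, from baseline (Visit 3) to end of treatment (Visit 5), in all patients with both measurements, the three subgroups pooled, two-sided 0.05, with a 95% confidence interval. The visit after discontinuation (Visit 6) is a secondary paired contrast against baseline.

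A pre-named Visit 3 to Visit 5 contrast in a repeated-measures or mixed model would also cure the defect. Pooling follows the total of 45 in section 4.2; if separate tests in each group of 15 are meant, the sentence should say so. The original scale is a choice the sponsor should confirm, because the target is expressed as a percentage.

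**Cost.** Wording only; visits and data are unchanged. At N = 45 under equal correlations, the paired test gives up about 4 points of power against the overall F-test alone if the effect fully reverses or persists (80% against 84%). It gains about 9 if half persists (80% against 71%). Against the overall test followed by the pre/post comparison it gains 4 to 10 points.

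**Separate points to settle at the same time.** How 0.05 is shared with GCSI is a different question. The Study Assessment and Monitoring list gives two gastric emptying measurements, whereas section 5.2, the visit schedule and section 7 give three. The schedule puts the washout visit at Day 51, which is 23 days after Day 28 and 20 days after Day 31, not four weeks. These passages need reconciling.

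### The emptying target is a percent change, but the planned ANOVA names no percent or log scale and no within-patient structure, and diagnoses are compared at time points rather than on change

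*Combined protocol and SAP*

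**What the plan says.** Gastric emptying is one of two primary endpoints (Section 3.3): "The second primary outcome measure will be the effect of VNS on gastric emptying time as measured by the gastric emptying spirulina breath test". Section 4.2 names the contrast, "Primary comparison: Gastric emptying half time score and GCSI, pre and post VNS", and gives the size of effect in relative terms: "To detect a clinically significant change of >30% in gastric emptying time". Enrolment is by diagnosis: "Total of 45 patients; 15 with functional dyspepsia, 15 with diabetic gastroparesis, and 15 with idiopathic gastroparesis".

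The analysis in Section 7 is one sentence: "Gastric emptying times will be plotted before treatment, at the end of treatment, and four weeks after end of treatment and compared by ANOVA". No transformation, percent change, ratio or confidence interval is given. Paired tests are named in the preceding sentences, which deal with the GCSI score; the emptying sentence names none. On the diagnoses, Section 7 says that "differences among the three subgroups of patients will be determined at baseline and after treatment". Objective 8 in Section 3.2 asks for something else: "Determine if there is a difference in response to VNS in patients with idiopathic vs. diabetic gastroparesis".

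**The concern.** There are two gaps between what the plan wants to know and what it says it will compute.

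- **The primary estimate.** A comparison of mean times over three visits does not return a percent change. A reader of the result could not say whether the target in Section 4.2 was met, or with what precision.
- **The comparison of diagnoses.** Comparing groups at baseline and again after treatment is not a comparison of response. A group that starts slower will probably still be slower afterwards, even if everyone improved equally. The documents give reason to expect unequal starting points: Section 1.1 ties gastroparesis to delayed emptying, while Section 3.1 adds functional dyspepsia because of shared symptoms and presumed mechanism. They give no comparable reason to expect idiopathic and diabetic patients to differ from each other at baseline.

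At stake are the interpretability of a primary endpoint and a possible false claim that VNS works better in one diagnosis than another.

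**Working it through.** **1. The plan's own figure.** The sample size of 45 (15 per diagnosis) cannot be reproduced, because no SD is given. Solved backwards for a two-sided paired t-test at 0.05, the largest SD of percent change that allows a mean 30% change to be detected is 30/d, where d is the detectable standardised effect:

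- n = 15: 38.6 points at 80% power, 33.3 at 90%.
- n = 45: 70.3 points at 80% power, 60.7 at 90%.

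Both power levels are shown because Section 4.2 prints a Type II error of 0.10, which implies 1 − 0.10 = 90%, beside 80% power.

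**2. Why scale matters for change.** The same 30% shortening is 0.30 × 80 = 24 minutes from a start of 80, 0.30 × 120 = 36 from 120, and 0.30 × 180 = 54 from 180. In minutes these are different responses. On the log scale each is ln(0.70) = −0.357.

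**3. Why the log scale does not rescue a post-treatment comparison.** Take baselines of 80 and 140 minutes. After an equal 30% shortening they are 56 and 98. The ratio is 140/80 = 1.75 before and 98/56 = 1.75 after. The baseline gap carries over intact on the log scale too.

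**4. Simulation.** From the documents: 15 per diagnosis and a 30% shortening. Assumed: lognormal half times; between-patient log SD 0.3–0.6; per-test log SD 0.2–0.3; geometric means of 80/120/150, 80/140/140 or 90/120/180 minutes; the same percent effect in every group; no dropout. Repeat runs move the ends of the ranges by a point or two.

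| Test, with identical 30% shortening | Raw | Log |
|---|---|---|
| Three diagnoses compared after treatment: rejects | about 46–100% | 61–100% |
| Three diagnoses compared on change: rejects | about 10–40% | about 5% |
| Two groups at 120 vs 150 or 180 min, compared on change: rejects | 6–20% | about 5% |
| Pre/post paired test, all 45: power | 99–100% | about 100% |

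With equal baselines the raw test of change rejects at about 5%. In the 80/140/140 scenario the two groups at 140 show no inflation on either scale.

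**5. Pairing against scale.** A separate simulation used medians 80/120/120, between- and within-patient CVs of 40%, n = 45, and half the effect persisting at follow-up. Repeated-measures ANOVA had 93% power raw and 97% log. A raw one-way ANOVA that ignores pairing had 68%. The scale costs about 97 − 93 = 4 points; ignoring pairing costs about 93 − 68 = 25.

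**6. The opposite assumption.** Suppose VNS removes 30 minutes from everyone. From 80 minutes that is 30/80 = 37.5%; from 180 it is 30/180 = 16.7%. With the same SDs and means, the log-scale three-group test of change rejects in about 22–59% of trials and the raw test in about 5%.

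**The case against.** The strongest reply is that the case for the log scale is built into the assumptions. Lognormal times and an exactly equal percent effect guarantee that logs behave well, and step 6 shows the reverse artefact under equal effects in minutes. A percentage used to describe a clinically important change does not by itself fix the analysis scale. This stands. It is why both scales should be reported, and why choosing logs has a real downside.

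It can also be said that this is a pilot (Section 3.1), that Section 7 never says the times are left untransformed, and that ANOVA may have been meant as repeated-measures. All true. But a primary endpoint needs its scale and pairing stated in advance, and silence leaves both to be chosen after the data are seen.

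Four stronger readings are tempting and are not supported:

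- **That the trial was sized on the 30%.** Section 4.2 states a target and shows no calculation.
- **That raw analysis is specified.** It is the natural reading of Section 7, but the scale is not stated.
- **That power is lost at the stated effect.** With all 45 pooled it is 99–100% on either scale under the main assumptions. The largest pooled loss in the wider simulation, 77% to 54%, needs CVs of 60% both between and within patients and medians of 70/140/140. The documents do not say that the pre/post test is powered within each diagnosis.
- **That the idiopathic vs diabetic answer will be wrong.** That contrast is distorted only if those two groups differ at baseline.

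**Conclusion.** The point holds in this form: the target is relative, while the analysis gives neither a relative estimate nor a within-patient structure, and the comparison of diagnoses is not a comparison of response. The first two follow from the text of Sections 4.2 and 7 alone. The third follows from setting Section 7 beside Objective 8.

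The most serious consequence is the post-treatment comparison of diagnoses. When baselines differ it rejects far above 5% although response is identical, and a log transformation alone does not cure that. The scale is a second, conditional problem that appears once change is tested. For pooled power, stating the pairing matters more than choosing the scale.

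The direction of these results follows from arithmetic. The sizes depend on assumed distributions, SDs and baseline means, and on whether the effect is proportional or additive, none of which the documents settle. This is worth correcting before analysis, but it does not stop the trial.

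**What to change.** In Section 7, replace the sentence on gastric emptying with a plan that:

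- analyses log gastric emptying half time in a repeated-measures model with visit, diagnosis and visit-by-diagnosis interaction, keeping each patient's visits linked;
- names end of treatment vs baseline as the primary contrast, and reports its geometric mean ratio as a percent change with 95% CI, so that it can be read against the 30% (a ratio of 0.70) in Section 4.2;
- tests Objective 8, for emptying, by the idiopathic vs diabetic contrast of that change within the interaction, and keeps the comparisons at single time points as description;
- reports change in minutes as a sensitivity analysis, and states that a difference between diagnoses seen on only one scale will be described as scale-dependent.

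Section 4.2 should also give the SD assumed for the change and reconcile the Type II error with the printed power.

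The cost is a few sentences, with no new data or visits. The downside is the one in step 6: if the true effect is a constant number of minutes, the log-scale interaction can mislead, which is why both scales must be shown.
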